7.5.3 Serious adverse events

Serious adverse events are defined by the Good Clinical Practice Guideline.

**SERIOUS ADVERSE EVENTS SHOULD BE IMMEDIATELY REPORTED
ACCORDING TO THE PROCEDURE DETAILED IN THIS PROTOCOL** (see chapter on Reporting adverse events)

7.5.4 Toxic deaths

Toxic death is defined as death due to toxicity. This must be reported on the summary form: the cause of death must be reported as "toxicity".

The evaluation of toxic deaths is independent of the evaluation of activity (patients can die from toxicity after a complete assessment of the effect of therapy).

7.5.5 Evaluability of toxicity

All patients receiving treatment will be considered evaluable for toxicity.

8 Statistical considerations

8.1 Statistical design

8.1.1 Sample size

This is a 2 by 2 factorial design with Overall Survival as the primary endpoint when comparing:

- Patients receiving RT alone or RT + adjuvant TMZ to those receiving RT & concurrent TMZ or RT & concurrent TMZ + adjuvant TMZ.

[Question I: test for superiority of the concurrent TMZ chemotherapy]

- Patients receiving RT alone and RT & concurrent TMZ to those receiving RT + adjuvant TMZ or RT & concurrent TMZ + adjuvant TMZ.

[Question II: test for superiority of the adjuvant TMZ chemotherapy]

The hypotheses are the following:

- In the EORTC trial 26951 for Anaplastic Oligodendroglioma and Oligoastrocytoma tumors, patients with no combined 1p/19q LOH treated by RT alone had a median survival of 24 months. In the EORTC trial 26882 for Anaplastic Astrocytoma, patients treated by RT alone had a median survival of 24 months.
- No interaction is anticipated between the concurrent and adjuvant temozolomide treatment that are assumed to contribute equally to the survival improvement.
- In the EORTC trial 26981, comparing RT & Concurrent TMZ + adjuvant to RT alone, the estimated Hazard Ratio was 0.63 and its 95% Confidence Interval [0.52-0.75].

The following table summarizes the statistical parameters of the design. A Hazard Ratio (HR) of 0.775 is assumed for both questions.

RT		No adjuv CT (median OS)	Adjuv CT (median OS)	Question I	
				Median OS	HR
No conc CT		24 m	31 m	(24+31)/2=27.5	0.775
Conc CT		31 m	40 m	(31+40)/2=35.5	
Question II	Median OS	27.5	35.5		
	HR	0.775			

For both questions, to detect a reduction of the risk of death of 22.5%, based on a two-sided logrank test, at an overall significance level of 5% and a power of 83%, a total of 534 events are needed. With an estimated accrual rate of 150 patients per year, a total of **748** patients should be recruited within approximately 5 years. A minimum follow-up of 2 ½ years will be needed to observe the required number of events. One interim analysis for efficacy is planned when 41% of the events have been observed (219). To perform this interim look, 11 additional events are necessary. Power of the trial was slightly increased in order to compensate for the loss of information due to patients dropping out before starting the adjuvant treatment. It is estimated that 10% of the patients will fail during or within the month following radiotherapy.

After evaluation of the first 183 patients entered, it appeared that the rate of patients not randomized was underestimated (45% vs 10%). The targeted registration sample size was re-estimated to approximately 1360. Recruitment will be continued till the planned **748** patients can be randomized.

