Objective(s)	
This trial is a follow up study of EORTC 26981 and of EORTC 26951 addressing the overall strategy of optimizing the treatment in newly diagnosed anaplastic glioma patients without combined 1p/19q loss. Patients will be randomized immediately after surgery to one of the four following therapeutic options:
 
Arm 1 : RT alone (and further treatment including chemotherapy at progression) Arm 2 : RT & concurrent CT Arm 3 : RT + adjuvant CT Arm 4 : RT & concurrent CT + adjuvant CT
 
Twelve months of adjuvant treatment is foreseen. Patients will be included based on the 1p/19q status of the tumor. Centers with known expertise in 1p/19q testing will be allowed to include patients based on local testing, with central review for 1p/19q testing (and histology). For sites without access to 1p/19q testing a central facility will be created. Methylation status of the MGMT promoter gene will be a stratification factor.
 
Primary objectives:
 
To assess whether concurrent radiotherapy with daily temozolomide chemotherapy improves overall survival as compared to no daily temozolomide in non-1p/19q deleted anaplastic glioma.
 
To assess whether adjuvant temozolomide chemotherapy improves survival as compared to no adjuvant temozolomide chemotherapy in non-1p/19q deleted anaplastic glioma

Methodology	Phase III – difference
Number of patients Number planned (Statistical design) Number analyzed	
This is a 2 by 2 factorial design with Overall Survival as the primary endpoint when comparing:
 
Patients receiving RT alone or RT + adjuvant TMZ to those receiving RT & concurrent TMZ or RT & concurrent TMZ + adjuvant TMZ.
 
[Comparison I]: test for superiority of the concurrent TMZ chemotherapy]
 
Patients receiving RT alone and RT & concurrent TMZ to those receiving RT + adjuvant TMZ or RT & concurrent TMZ + adjuvant TMZ.
 
[Comparison II]: test for superiority of the adjuvant TMZ chemotherapy]
 
For both comparisons, to detect a reduction of the risk of death of 22.5% based on a two-sided logrank test, at an overall significance level of 5% and a power of 83%, a total of 534 events are needed. With an estimated accrual rate of 150 patients per year, a total of 748 patients can be recruited in 5 years. A minimum follow-up of 2 ½ years will be needed to

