8.3 Interim analyses

8.3.1 Original plan

One formal interim analysis is planned for both questions when 219 events (41%) have been observed. Based on the assumption of the statistical design, the interim analysis should take place approximatively 4 years after the start of the trial when about 600 patients have been recruited.

Only the rejection of H_0 , the hypothesis of no efficacy, will be considered. Based on stopping boundaries from the Rho family ($Rho=2$), at the interim analysis, the nominal significance level for rejecting H_0 will be of 0.0084. The final analysis will be performed at a significance level of 0.0453. Power simulations were performed with EAST v 4.0.1.34 the results are presented in the table below based on 10000 simulations.

Scenario	Prob. of rejection of H0		Overall Power
	Interim analysis	Final analysis	
HR=0.63 (-ln(HR)=0.462)	79%	21%	99.9%
HR=0.775 (-ln(HR)=0.255)	23%	61%	83%
HR=0.80 (-ln(HR)=0.223)	16%	56%	72%
HR=0.825 (-ln(HR)=0.192)	11%	47%	59%

The probability of early stopping the assumption of the design is 23% at the interim analysis and 61% at the final analysis. The design still performs well if the true treatment effect is somewhat smaller than expected: for HR=0.80 the overall power is 72% with a 16% probability of early stopping at the interim analysis. For the pessimistic scenario of HR =0.825 the design will have a poor performance and the overall power will drop to 59%. Should the true difference between the treatment arms be comparable to the one observed in the EORTC 26981 (HR=0.63) trial, the probability of early stopping after the interim look increases to 79%.

The opportunity to stop the trial for futility (rejection of H1) was investigated. It was not possible to find a design allowing for rejection of H1 with sufficient power at an appropriate time of assessment before the end of the accrual period.

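### The slight increase in power does not make up for a 10% loss before adjuvant treatment: Question II has about 75% power, not 83%, if those patients gain no adjuvant effect

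*Combined protocol and SAP*

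**What the plan says.** Section 8.1.1 sizes both factorial questions alike: "A Hazard Ratio (HR) of 0.775 is assumed for both questions", and "based on a two-sided logrank test, at an overall significance level of 5% and a power of 83%, a total of 534 events are needed". An interim efficacy look is set at 219 events, and "To perform this interim look, 11 additional events are necessary". The Protocol summary repeats the 83% for both comparisons.

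On loss before adjuvant treatment, section 8.1.1 says: "Power of the trial was slightly increased in order to compensate for the loss of information" caused by dropout before that treatment starts. It then adds: "It is estimated that 10% of the patients will fail during or within the month following radiotherapy". The section gives neither the power before the increase nor the power intended after the loss, shows no diluted HR, and does not define failure.

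Sections 8.2.2 and 8.2.3.1 place the efficacy analyses in the intention-to-treat population, as allocated. In section 8.3.1, "at the interim analysis, the nominal significance level for rejecting H_0 will be of 0.0084" and the final level is 0.0453. The table there gives power of 83% at HR 0.775, 72% at 0.80 and 59% at 0.825.

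**The concern.** A patient allocated to adjuvant temozolomide who never starts it remains in the adjuvant group, and the death still counts towards the 534. The patient carries no adjuvant effect. The loss therefore shrinks the log HR; it does not simply remove events. Power depends on the square of the log HR, so a 10% shrinkage needs events multiplied by 1/0.9² = 1.23, more than a slight increase in power would be expected to cover.

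At stake is a stated property of the design for one of the two primary questions: a reader of section 8.1.1 would conclude that the expected early loss has been covered. Only Question II is affected, because concurrent temozolomide is given during radiotherapy.

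**Working it through.** **Inputs.** HR 0.775, 534 events, two-sided 5%, interim at 219 events, 11 added events, 748 patients, 10% early failure, and median survival of 24, 31, 31 and 40 months in the four arms (section 8.1.1). Nominal levels 0.0084 and 0.0453 (section 8.3.1).

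**1. Reproduce the plan.** Schoenfeld's formula gives 4(z₀.₉₇₅ + z₀.₈₃)²/(ln HR)² = 4(1.960 + 0.954)²/0.2549² = 523 events. Adding 11 gives 534, as stated.

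For the two-look design, the logrank statistic at d events has mean √(d/4) × (−ln HR). The correlation between looks is √(219/534) = 0.640, and the critical values are 2.636 and 2.002. At HR 0.775 the means are 1.886 and 2.945. Overall alpha is 0.0500 and power is 83.0%, with 22.7% at the interim. The same calculation gives 72.2% at HR 0.80 and 59.3% at 0.825, matching section 8.3.1.

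**2. Ten per cent never start and gain nothing.** ln HR = 0.9 × (−0.2549) = −0.2294, so HR = 0.795. The means become 1.697 and 2.651, and power is **74.6%**. The plan's own table, interpolated, agrees: 83 − 11 × (0.020/0.025) = 74.2%.

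**3. Lower end: all early failures die before adjuvant treatment.** 748 × 0.10 ≈ 75 deaths, and 75/534 = 14% of events carry no effect. HR = 0.775^0.86 = 0.803, and power is **70.7%**.

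**4. Upper end: only the deaths expected by then are uninformative.** Radiotherapy plus rest is 6.5 + 4 = 10.5 weeks, or 2.41 months. With exponential survival (assumed), the proportion dead is 1 − 2^(−2.41/median): 6.7%, 5.3%, 5.3% and 4.1%, mean 5.3%. That is about 40 patients, and 40/534 = 7.5% of events. HR = 0.775^0.925 = 0.790, and power is **76.9%**.

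**5. Simulation.** The 2×2 trial was simulated 4,000 times per scenario, with a standard error of about 0.7 points.

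| Scenario | Power |
|---|---|
| No dilution | 82% |
| 10% non-starters, otherwise normal survival | 73% |
| 10% early progressors, median survival 6–12 months (assumed) | 73–74% |
| 10% early deaths | 70% |

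**6. What a slight increase could offset.** Section 8.1.1 gives no starting power. If it was 80%, two-look power at 534 events falls from 83% to 80% when the log HR is multiplied by 0.961. The increase thus covers about 4% dilution, not 10%. With 10% dilution, 80% power would need 484/0.81 = 598 events, or 598 × 534/523 ≈ 611 with the interim look. For 83% the figure is about 660.

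**7. A possible origin.** Treating the loss as missing events gives 484/0.9 = 538, close to 534. Conversely, 534 × 0.9 = 481 events give about 79–80% power. That would suit events lost from the analysis, but not an intention-to-treat analysis that keeps them.

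**The case against.** **The plan does not claim 83% after dropout, nor a step from 80% to 83%.** A reader might infer both. The documents support neither: section 8.1.1 says only that the increase was slight, and 80% appears only in section 8.3.2, for the concurrent question. This stands, but the 83% versus 75% comparison does not use the 80%.

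**Ten per cent is not a minimum dilution.** A reader might take the log HR to shrink by at least that much. Failure is undefined. Section 7.1.2 reserves early cancellation of adjuvant treatment for exceptional cases, and section 7.1.2.1 keeps patients with radiological progression alone on it. Some early failures would therefore start. This stands, and it is why the range reaches 77%. Likewise 71% is an extreme, since it requires about 75 early deaths where the plan's medians imply about 40.

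**0.775 may already be the intention-to-treat effect.** Section 8.1.1 does not say. If so, 83% holds, but there is then no dilution left for the increase to offset.

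**The sensitivity is tabulated and the question is closed.** Section 8.3.1 shows 72% at HR 0.80. In section 8.3.2 the data monitoring committee recommends releasing the adjuvant results, and Appendix M records that enrolment and treatment are complete. This lowers the severity. Nothing in the plan, however, links the lower power to the expected dropout.

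**Conclusion.** The point holds as a minor correction. On the natural reading, the increase does not compensate for the stated 10% loss: Question II power is about 75%, within a range of 71–77% set by what failure means. This rests on three assumptions: 0.775 is the effect in patients who start, those who never start gain no adjuvant effect, and analysis takes place at 534 deaths with early deaths included.

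Two stronger readings should not be drawn. Planning power does not alter how the adjuvant result is interpreted, since an observed effect is judged from its HR and confidence interval. The 45% versus 10% figure in section 8.1.1 is also separate: it concerns registered patients who were not randomized.

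**What to change.** In section 8.1.1 and the Protocol summary:

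- State that 83% for Question II is the power before loss of patients who never start adjuvant treatment.
- Give about 75% as the power with 10% non-starters, and the range 71–77% with the assumption behind each end.
- Define failure during or shortly after radiotherapy, and say whether 0.775 is the effect in starters or by allocation.
- Delete the statement that the increase compensates, or correct it by giving the power before the increase and after the loss.

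The cost is wording only, and a less favourable stated power for Question II. No patients or events are added, and Question I is untouched.

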8.1.2 Randomization and stratifications

Patients will be centrally randomized (for practical details, see chapter on registration / randomization procedure). A minimization technique will be used for random treatment allocation stratifying by:

- Institution,
- WHO Performance Status (0 vs >0),
- Age (≤ 50 vs > 50),
- The presence of 1p LOH only (yes vs no) ,
- The presence of oligodendroglial elements (yes vs no) and
- MGMT promoter methylation status (methylated vs unmethylated vs indeterminate).

8.2 Statistical analysis plan

8.2.1 Primary and secondary endpoints

8.2.1.1 Overall survival (primary endpoint)

Overall Survival (OS) is calculated from the date of randomization up to the date of death (any cause). For patients still alive at the time of analysis, OS will be censored at last follow-up visit date.

8.2.1.2 Progression-free Survival (secondary endpoint)

The Progression-free Survival (PFS) is calculated from the date of randomization up to the date of first progression or death (any cause) whichever comes first. In case a patient is still alive and without progression at the last follow up visit date, PFS will be censored at the date of last follow up visit date.

8.2.1.3 Neurological deterioration-free survival (secondary endpoint)

The neurological deterioration-free survival (NPFS) is calculated from the date of randomization up to the date of first neurological deterioration (see section 7.2) or death (any cause) whichever comes first. In case a patient is still alive and without neurological deterioration at the last date of assessment of the WHO performance status, NPFS will be censored at that date.

8.2.1.4 Toxicity (secondary endpoint)

The assessment of safety will be based on the frequency of Adverse Events graded according to the NCI-CTCAE version 3.0 scoring system.

8.2.1.5 Mini Mental State Examination (MMSE) (secondary endpoint)

The Mini Mental State Examination (MMSE) is a brief, standardized tool to grade patients' cognitive function. It is an 11-question measure that tests five areas of cognitive function: orientation, registration, attention and calculation, recall, and language. The maximum score is 30. Since its creation in 1975 by Folstein et al (Ref. 20), the MMSE has been validated and extensively used in both clinical practice and research. Following Tangalos et al. (Ref. 21) and as previously used by Brown et al (Ref. 22) a decline of more than 3 points in the MMSE score will be considered to represent clinically significant deterioration. Following Brown et al, the patient's cognitive function will be considered 'impaired' if the MMSE score is 26 or less and 'normal' if it is 27 or more. MMSE questionnaire can be found in Appendix L.

8.2.2 Analysis populations

- Intention-to-treat population: All randomized patients will be analyzed in the arm they were allocated by randomization.
- Per protocol population: All patients who are eligible (including 1p/19q LOH status at central review) and have started their allocated treatment (i.e. RT started in all arms).
- Safety population: All patients who have started their allocated treatment (i.e. RT started in all arms). The safety of patients excluded from the safety population is separately reported.

A patient will be considered to be eligible if he/she did not have any major deviations from the patient entry criteria listed in chapter 3 of the protocol. Eligibility will be assessed by the Study Coordinator based on the review of each patient file.

8.2.3 Statistical methods

8.2.3.1 Analyses populations

All the analyses of the efficacy endpoints (overall survival and progression-free survival) will be performed in the intention-to-treat population.

All the analyses of the safety endpoints will be performed in the safety population.

8.2.3.2 Analyses methods for efficacy endpoints

For the primary analysis of overall survival and progression-free survival, the Cox proportional hazards model will be fitted with a question indicator variable (one for each question, I and II) and adjusted by the stratification factors at randomization. For overall survival the nominal significance level to be used at the interim look and final analysis is described in section 8.3 below.

In the final report, important secondary analyses of overall survival will be 1) the Cox models with adjustment of the questions by MGMT promoter methylation status after randomization and the other stratification factors. 2) the Cox models with adjustment of the questions by IDH1 mutation status (in replacement of MGMT promoter methylation status) and the other stratification factors. Significance level used for these two secondary analyses is the same as for the primary analysis. All analyses of progression free survival will be performed at a 5% significance.

The Kaplan-Meier technique will be used to obtain estimates of the overall survival and progression-free survival. The hazard ratios will be estimated with their 95% confidence intervals. Medians will be presented with 95% confidence interval provided by the Reflected Method (Ref. 23). 5 year survival and progression-free survival rates will be presented with 95% confidence interval calculated by Greenwood formula's estimation of the standard deviation.

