Statistical methods	
For the primary analysis of OS and PFS, two-sided superiority logrank tests will be computed at an overall significance level of 5%.
 
The Kaplan-Meier technique will be used to obtain estimates of the OS and PFS.
 
The Cox proportional hazard model will be fitted with the treatment and the following adjustment factors: WHO performance status (PS 0 vs >0), Age (<=50 vs >50), Presence of 1p loss (Yes vs No), Presence of oligodendroglial elements (Yes vs No). The MGMT promoter methylation status will be used as a stratification factor.
 
Changes in MMSE scores over time will be analyzed. The distributions in treatment arms will be compared at each evaluation point using a Chi-square test for trend. A Bonferroni adjustment of the type I error rate will be used to correct for multiple tests.

Central pathology Translational research	
Central pathology review will be performed.
 
Upfront assessment of 1p/19q LOH is mandatory
 
Following registration of the patient as soon as possible after surgery the following material must be sent:
 
A paraffin embedded tumor sample (preferably a tumor block, otherwise 30 unstained slides)
 
20 ml whole blood collected in an EDTA tube
 
the pathology review and 1p/19q review reports
 
Following central pathology review, central 1p/19q assessment, MGMT promoter methylation status determination and IDH mutation analysis, the H&E stained slides will be entered into the EORTC virtual tumor bank.

Quality of Life	
The main objective of QoL assessment within this clinical trial is to determine the impact of no adjuvant chemotherapy versus adjuvant therapy until progression for anaplastic glioma on overall health/QoL. Based on the recent EORTC study 26981, the hypothesis is that we expect no differences between arms using the global QOL scale during treatment, but there may be a later benefit to the adjuvant therapy arm if disease progression is achieved, thereby leading to a better global QOL.

Trial organization

- This trial is an Intergroup Trial, jointly conducted by several national/international cancer clinical research groups in different countries of European Union and third countries.
- Each participating group is the Sponsor for their participants (unless otherwise agreed).
- In summary:

Country	Recruiting group(s)	Sponsor
Canada	NCIC	NCIC
United Kingdom	MRC	EORTC
United States	RTOG	RTOG
Australia/New Zealand	COGNO CTC	COGNO CTC

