2.3.2 Secondary endpoints

Secondary endpoints of the study are progression free survival, neurological deterioration free survival, quality of life, toxicity, and development of cognitive deterioration.

3 Patient selection criteria

All patients are initially registered into the trial as soon as possible after surgery. After this point, material must be sent for 1p/19q analysis and MGMT promoter methylation assay. This should again be done as soon as possible. Patients can only be randomized into the trial within 8 days from the start of radiotherapy; at this time, all baseline requirements for the study must have been fulfilled.

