8.3.2 New plan

Further to the original interim analysis, the IDMC formulated the following recommendations:

- To release and publish the results on all endpoints for the adjuvant TMZ comparison without delay.
- In doing, so, to pay particular attention to the impact on patients in arms 1-2, who may benefit from initiating adjuvant TMZ and for whom a therapeutic decision to initiate such treatment may ensue. In particular, those patients who are still receiving RTX (with or without concomitant TMZ), as well as those patients who have finished RTX treatment within the past three months.
- To continue the follow-up for the concurrent TMZ question. Because of the very long follow-up time required to reach data maturity for overall survival for this question, consideration may be given to implementing a further interim analysis. The IDMC would welcome proposals for a revised plan incorporating a second such interim analysis.
- To take the necessary steps to obtain data on the MGMT promoter status for all patients, including reanalysis of samples using more modern assays that may require less material than the early assays. The investigators should assess heterogeneity of results across subgroups.

A new interim analysis plan was designed by an independent statistician. It includes an additional interim analysis for both efficacy and futility analysis at 2/3 of information (356 deaths) using the original spending function (stopping boundary from Rho family ($Rho=2$)) for the efficacy and an O'Brien Fleming stopping boundary for futility. This analysis will be binding in order to keep the same number of events and the 80% power at the final analysis. Based on these new assumptions, the trial will be stopped for futility if $HR \geq 0.882$ and for early efficacy if $HR < 0.778$. $HR=0.882$ corresponds to OS rate at 2 years of 71.9% in the no concurrent TMZ chemotherapy arm versus 74.7% in the concurrent TMZ chemotherapy arm (less than 3% difference observed). The timing of this second interim analysis is at about 35 months after end of accrual i.e. September 2018. The final analysis is expected in 2022 at will be performed at a significance level of 0.044 ($HR < 0.841$).

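### The summary promises an overall 5% level for progression-free survival, but section 8.2.3.2 puts every PFS analysis at a flat 5% and gives no levels by look

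*Combined protocol and SAP*

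**What the plan says.** - **Protocol summary, statistical methods:** "For the primary analysis of OS and PFS, two-sided superiority logrank tests will be computed at an overall significance level of 5" per cent. The overall level covers both endpoints.
- **Section 8.2.3.2:** "For overall survival the nominal significance level to be used at the interim look and final analysis is described in section 8.3 below". For PFS the rule is different: "All analyses of progression free survival will be performed at a 5% significance".
- **Section 8.3.1:** "One formal interim analysis is planned for both questions when 219 events (41%) have been observed". Nominal levels of 0.0084 (interim) and 0.0453 (final) follow. The counts that trigger the looks, the levels and the hazard-ratio cut-offs in section 8.3 all concern OS.
- **Section 8.3.2:** after that interim, the IDMC's first recommendation was "To release and publish the results on all endpoints for the adjuvant TMZ comparison without delay". For the concurrent question, a second interim at 356 deaths was added, with a final level of 0.044.
- **Section 12.1.2:** the Final Analysis Report summarises all data collected. Section 8.2.3.2 fits the primary PFS model with an indicator for each of the two questions.
- **Section 2.3.2:** PFS is a secondary endpoint, the first one listed.

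**The concern.** The plan states a property (overall 5% for PFS) and a rule (5% for each PFS analysis). The rule delivers the property only if each question has a single formal PFS test, and the plan nowhere limits PFS to one. For the adjuvant question, two analyses can be foreseen from the text: the recommended release after the first interim, and the final report. For the concurrent question, the plan does not say what status PFS has at the interims.

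A PFS result could be claimed on its own. Sections 1.1.3 and 1.1.4 suggest that delaying progression may help patients even without a survival gain. Section 10.1 says that longer PFS would become a goal in itself if it proves to preserve quality of life. Without a rule, a reader of a published PFS p-value cannot tell which error rate stands behind it.

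**Working it through.** **Inputs from the documents.** 219 of 534 events at the first interim, fraction t = 219/534 = 0.410; 356 of 534 at the second, t = 0.667; Rho = 2 spending; OS levels 0.0084, 0.0453 and (new plan) 0.044; HR 0.775 (design) and 0.63 (optimistic case). **Not in the documents, so assumed:** PFS information fractions and the OS-PFS correlation.

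**1. The plan's OS figures reproduce.**
- Interim spend: 0.05 × (219/534)² = 0.05 × 0.1682 = 0.0084.
- Solving the two-look bivariate normal (correlation √0.410) gives a final level of 0.0453, as stated.
- Power at HR 0.775 with 534 events is 83.0%, with 22.7% crossing at the interim (stated: 83% and 23%).
- Adding the look at 0.667 gives a nominal level of 0.0177, that is HR = 0.778, which matches section 8.3.2.

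So the OS scheme is sound, and the same method can be applied to PFS.

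**2. PFS tested at 5% at each look, any one significant result being enough.** Error = 1 − P(|Z_k| < 1.96 at all looks), with corr(Z_i, Z_j) = √(t_i/t_j).

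| PFS fractions | Error per question |
|---|---|
| 0.41, 1 (as for OS) | 8.6% |
| 0.5, 1 | 8.3% |
| 0.7, 1 | 7.6% |
| 0.9, 1 | 6.5% |
| 0.41, 0.667, 1 (as for OS) | 10.3% |
| 0.5, 0.75, 1 | 9.7% |
| 0.6, 0.8, 1 | 9.1% |
| 0.9, 0.95, 1 | 6.9% |

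Progressions come before deaths, so the PFS fractions are probably higher than those for OS and the error is nearer the lower ends.

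**3. Interim PFS read only if OS crosses 0.0084, then tested again later.** PFS has no effect; the OS drift is −ln(HR) × √534 / 2, which is 0 at HR 1, 2.95 at HR 0.775 and 5.34 at HR 0.63. First PFS fraction 0.41 to 0.8 and OS-PFS correlation 0 to 0.8 were simulated.

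| OS effect | Error per question |
|---|---|
| none | 5.0-5.4% |
| HR 0.775 | 5.5-6.7% |
| HR 0.63 | 6.1-7.8% |

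Hand check at correlation 0 and fraction 0.41: error = 0.05 + P(OS crosses) × (0.086 − 0.05). At HR 0.63, with 78% crossing, this is 0.05 + 0.78 × 0.036 = 0.078.

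**4. One PFS test per question, at the look where OS is decided.** About 5.0% to 5.9%. The small excess arises because the timing depends on a correlated endpoint; the 5.9% needs an assumed correlation of 0.8.

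**5. PFS with its own Rho = 2 levels.**
- 0.0084/0.0453 for two looks: 5.0% at OS fractions.
- 0.0084/0.0177/0.0390 for three looks: 5.0% at OS fractions, with no credit for futility stopping.
- Both fall below 5% at the later PFS fractions tried.
- Borrowing the plan's 0.044 as the third level (0.0084/0.0177/0.044) gives 5.4% at OS fractions. That level belongs to a design with a binding OS futility rule, and such credit does not automatically carry over to PFS.

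**The case against.** The strongest reply is that no interim PFS test is scheduled. The looks in section 8.3 are OS looks. The sentence on PFS closes a paragraph that opens with the final report and lists alternative covariate adjustments, so it may mean every version of the PFS model, not every look. One primary PFS test per question at 5% would satisfy both the summary and section 8.2.3.2. Accumulating data generally stay confidential (section 9.2.2), PFS is secondary, and no stopping rule uses it.

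Much of this stands. A reader might infer that PFS is tested at every look and that its true error is 8-10%. The documents do not support that. They schedule no such tests, and the three-look case for the concurrent question is an inference. The only recorded early release concerns the adjuvant question. It followed an IDMC recommendation after an OS look, and gating on OS lowers the error. Sections 1.1.3 and 10.1 also hedge the clinical value of PFS.

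What does not stand is that the wording is therefore adequate. The one-test reading is compatible with the text but is not stated in it, and the recommended early release together with the final report already makes two adjuvant PFS analyses foreseeable.

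**Conclusion.** The point holds as a mismatch between a promised property and the rule meant to deliver it. The size is conditional. Per question, the PFS error is:

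- about 5% if PFS is formally tested once;
- about 5-8% if interim PFS is read only after OS crosses and is then retested;
- about 6.5-8.6% with two unadjusted tests;
- about 7-10% with three, a case open only to the concurrent question.

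These ranges rest on assumed PFS information fractions and, in the gated case, on an assumed OS-PFS correlation and OS effect. No single figure can be called the true error. The OS analysis is not affected.

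**What to change.** Replace the PFS sentence in section 8.2.3.2 with:

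> PFS is formally tested once per question at two-sided 5%, at the analysis where OS for that question is decided; all other PFS analyses are descriptive.

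Alternatively, give PFS its own Rho = 2 levels: 0.0084/0.0453 for two looks, or 0.0084/0.0177/0.0390 for three, with no credit for OS futility. Do not reuse 0.044 as the third PFS level. Align the summary with whichever is chosen.

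The first interim is past, so the amendment should say that the rule was set after it, and should name the analysis that counts as the formal PFS test for the adjuvant question.

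The cost is wording only, with no change to events or follow-up. Later PFS p-values become descriptive, or face a slightly stricter threshold. The one-test rule can run slightly above 5% (at most 5.9% in the cases tried). If strict control is wanted, the level-by-look option is the safer one.
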